08 MAR 2017

[Redacted] DSE GmbH, EU B&DO, Study Data Manager

[Redacted]

01/03/2017

[Redacted] Coordinating Investigator
The Coordinating Investigator will sign the Clinical Study Report
on behalf of all Investigators.

[Redacted]

05 06 2018

[Redacted] Coordinating Investigator
The Coordinating Investigator will sign the Clinical Study Report
on behalf of all Investigators.

[Redacted]

dup 03 2017
not filled out

PROTOCOL SYNOPSIS

EudraCT Number:	2016-002683-14
-----------------	----------------

Protocol Number:	DSE-EDO-01-15-EU
------------------	------------------

Investigational Product:	Edoxaban (DU-176b)
---------------------------------	--------------------

Active Ingredient(s)/ international non-proprietary name:	N-(5-Chloropyridin-2-yl)-N'-[(1S,2R,4S)-4-(N,N-dimethylcarbamoyl)-2-(5-methyl-4,5,6,7-tetrahydro[1,3]thiazolo[5,4-c]pyridine-2-carboxamido)cyclohexyl]oxamide mono (4-methylbenzenesulfonate) monohydrate/Edoxaban
---	--

Study Title.:	Evaluation of the safety and efficacy of an edoxaban-based compared to a vitamin K antagonist-based antithrombotic regimen following successful percutaneous coronary intervention (PCI) with stent placement. Edoxaban Treatment versus VKA in patients with AF undergoing PCI (ENTRUST-AF PCI)
---------------	--

Study Phase:	Phase 3b
--------------	----------

Indication Under Investigation:	Subjects with atrial fibrillation (AF) following successful PCI with stent placement.
---------------------------------	---

Study Objectives:	
The primary objective is to compare a 12-month antithrombotic regimen of edoxaban in combination with clopidogrel or another P2Y₁₂ antagonist against a regimen of a vitamin K antagonist (VKA) in combination with clopidogrel or another P2Y₁₂ antagonist and 1-12 months ASA in subjects with AF following successful PCI with stent placement in terms of the incidence of major or clinically relevant non-major ISTH-defined bleeding (MCRB).
 
There are two primary hypotheses for bleeding to be tested consecutively in this study.
 
• The edoxaban-based antithrombotic regimen is non-inferior to the VKA-based antithrombotic regimen with regards to MCRB.• The edoxaban-based antithrombotic regimen is superior to the VKA-based antithrombotic regimen with regards to MCRB.
-------------------	--

These two hypotheses are tested in a hierarchical manner, non-inferiority followed by superiority to control the type-I error rate, with adequate power for each of the two hypotheses.

Secondary exploratory objectives of the study are to compare the edoxaban-based anticoagulation regimen to the VJ (aspirin) antithrombotic regimen with regard to:

- Main efficacy endpoint (MEE), defined as the composite of cardiovascular (CV) death, stroke, systemic embolic events (SEE), spontaneous myocardial infarction (MI) and definite stent thrombosis.
- Net clinical benefit (NCB), defined as the composite of CV death, stroke, SEE, spontaneous MI, definite stent thrombosis and ISTH-defined major bleeding.
- Main thromboembolic event, defined as composite of cardiac or thromboembolic death (thromboembolic death considered to be thromboembolic in Origin (including thromboembolic stroke, pulmonary embolism, any other systemic embolism), ischemic stroke, SEE, spontaneous MI and definite stent thrombosis.
- ISTH-defined major bleeding
- Any bleeding defined as the composite of major, clinically relevant non-major and minor bleeding (ISTH definition)
- Symptomatic intracranial hemorrhage (ICH)
- Composite of stroke and SEE
- Composite of all-cause death, stroke, SEE, spontaneous MI and definite stent thrombosis
- Composite of CV death, spontaneous MI and definite stent thrombosis
- The single components of the composite primary and secondary endpoints mentioned above are explored.
- Safety parameters such as (serious) adverse events, laboratory parameters, ECG and vital signs.

Study Design: This is a multinational, multicenter, randomized, open-label Phase 3b study with blinded evaluation of endpoints by an independent Clinical Event Committee (CEC) [PROBE design]. An

independent Data and Safety Monitoring Board (DSMB) is responsible for monitoring safety during the study.

Subjects eligible to participate in the study provide written informed consent (IC) before randomization or any study-specific procedures. Once written IC is obtained, subject should be randomized without delay via an interactive voice and web response system (IXRS).

The Investigator should be prepared to provide subject information, including, but not limited to: age, body weight, clinical presentation (ACS or stable coronary disease), CrCL using Cockcroft-Gault formula and CKD-EPI Equation for estimating GFR on the Natural Scale (see Section 17.6) and whether the subject is taking certain concomitant P-gp inhibitors (see Section 5.3.1).

Randomization is stratified by clinical presentation (ACS or stable coronary disease), requirement for dose adjustment of edoxaban (60 or 30 mg), and geographical region. Subjects are assigned randomly via the above mentioned IXRS such that the study has a 1:1 ratio of subjects in the two antithrombotic treatment regimens:

- Edoxaban-based regimen for 12 months:

1. Edoxaban 60 mg once-daily or 30 mg once-daily in selected subjects (see below "Dosage Form, Dose, and Route of Administration" and Section 5.3.1).
2. Clopidogrel 75mg once-daily (or in the presence of a documented clinical need prasugrel [5mg or 10 mg once-daily] / ticagrelor [90 mg twice-daily] may be used).

The use of a P2Y₁₂ antagonist other than clopidogrel must be pre-declared.

3. Concomitant use of another anti-platelet agent (i.e. ASA) is **not** allowed.

- VKA-based regimen for 12 months:

1. The VKA of choice with once-daily dosing for target international normalized ratio (INR) between 2.0 to 3.0, inclusive.
2. Clopidogrel 75mg once-daily (or in the presence of a documented clinical need prasugrel [5mg or 10 mg once-daily] / ticagrelor [90 mg twice-daily] may be used).

3. ASA (100 mg once-daily) for a minimum of 1 month and up to 12 months duration at the Investigator discretion guided by the clinical presentation (ACS or stable coronary disease), and upon the CHA₂DS₂-VASc and HAS-BLED score. (1}

4. If the use of a P2Y₁₂ antagonist other than clopidogrel must be pre-declared, together with the intended duration of ASA treatment.

All dosage adjustments are implemented through the IXRS. The IXRS provides the appropriate drug supply kit number based on the subject's information as provided by the Investigator.

Note: For simplicity, this protocol uses the term "edoxaban" to refer to edoxaban tosylate, "clopidogrel" to refer to clopidogrel bisulfate and the term " prasugrel" to refer to prasugrel hydrochloride.

Study Duration: The assigned regimens (edoxaban-based or VKA-based) are continued for 12 months and all subjects are followed for 12 months irrespective of permanent or temporary changes in the antithrombotic regimen. Clinical follow-up is only terminated at the explicit documented request of the subject. All subjects on edoxaban or VKA at 12 months, have a contact planned 30 days after the end-of-treatment (EOT) visit, to collect data on targeted concomitant medications, SAEs, and other safety events of interest. The overall duration of subject participation from screening through follow-up is therefore approx. 13 months.

Study Sites and Location: It is planned to enroll 1500 subjects (750 per antithrombotic regimen) in at least 150 study sites in Europe, and Asia-Pacific.

Subject Eligibility Criteria: OAC indication for atrial fibrillation for a period of at least 12 months following successful PCI with stenting in adult male and female patients ≥18 years of age.

Eligibility of pre-screened subjects is assessed 4 hours after sheath removal and within 5 days after successful PCI. If a staged PCI is planned, eligibility is assessed after completion of the last stage.

A clinically successful PCI requires both anatomic and procedural success along with relief of signs and/or symptoms of myocardial ischemia at the time of randomization (for details see Section 4.1.1).

Subjects who meet any of the following criteria are ineligible for the study:

Bleeding risks or systemic conditions

1. Known bleeding diathesis, including but not limited to,
 - a. Uncontrolled active bleeding, encompassing both ISTH-major and clinically-relevant non-major bleeding, at the time of randomization.
 - b. Lesion or condition, if considered to be a significant risk for major bleeding.

This may include but is not limited to: unresolved gastrointestinal ulceration, presence of malignant neoplasms at high risk of bleeding (e.g. malignancies with metastasis), recent unresolved brain or spinal injury, recent brain, spinal or ophthalmic surgery, any intracranial hemorrhage, known or suspected esophageal varices, arteriovenous malformations, vascular aneurysms (of more than 3.5 cm) or major intraspinal or intracerebral vascular abnormalities.

Medication-related

2. INR > 2.5 (the subject can be reconsidered at a later point in time, but within 5 days of sheath removal).
3. Contraindication to edoxaban, VKA, ASA and/or P2Y₁₂ antagonists;
4. Concomitant treatment with other antithrombotic agents, fibrinolytic therapy and chronic nonsteroidal anti-inflammatory drugs (NSAIDs).

Concomitant conditions and therapies

5. Critically ill or hemodynamically unstable subjects (at the time of randomization) including:
 - a. cardiogenic shock or acute decompensated heart failure, with the requirement for vasopressor agents or inotropic support or mechanical support to support circulation
 - b. respiratory failure requiring endotracheal intubation and mechanical ventilation.
6. Any prior mechanical valvular prosthesis;

-
7. Planned coronary or vascular intervention or major surgery within 12 months; Randomization must be deferred to the last stage in a multistep, multivessel PCI procedure;
 8. Moderate or severe mitral stenosis;
 9. Ischemic stroke within 2 weeks prior to randomization;
 10. Uncontrolled severe hypertension with a systolic blood pressure (BP) ≥ 180 mmHg and/or diastolic BP ≥ 120 mmHg;
 11. End stage renal disease (ESRD) (CrCL < 15 mL/min) or on dialysis;
 12. Known abnormal liver function prior to randomization (incl. hepatic disease or biochemical evidence of significant liver derangement known prior to randomization) (see appendix 17.4).

Other exclusion criteria

13. Any of the following abnormal local laboratory results prior to randomization:
 - a. Platelet count $< 50 \times 10^9/L$
 - b. Hemoglobin < 8 g/dL
 14. Unable to provide written informed consent (IC);
 15. Female subjects of childbearing potential without using highly effective contraception (female of childbearing potential is defined as one who has not been postmenopausal for at least one year, or has not been surgically sterilised, or has not had a hysterectomy at least three months prior to the start of this study). Females taking oral contraceptives should have been on therapy for at least three months. Adequate contraceptives include: Combined (estrogen and progestogen containing) oral, intravaginal or transdermal hormonal contraception associated with inhibition of ovulation; progestogen-only oral, injectable or implantable hormonal contraception associated with inhibition of ovulation; intrauterine device (IUD); intrauterine hormone-releasing system (IUS); bilateral tubal occlusion; vasectomized partner; sexual abstinence
 16. Pregnant or breast-feeding subjects;
 17. Assessment that the subject is not likely to comply with the study procedures or have complete follow-up;
-

-
18. Currently participating in another clinical trial that potentially interferes with the current study;
 19. Previous randomization in this study;
 20. Active on prescription drug abuse and addiction; abuse of illicit substances (i.e. marijuana, cocaine, methamphetamine, heroin) and alcohol abuses during the last 12 months according to the judgement of the investigator
 21. Life expectancy < 12 months.

Dosage Form, Dose, and Route of Administration:

Edoxaban: 60, 30 and 15 mg provided as film coated tablets for oral use.

Subjects receive 60 mg edoxaban once-daily. A dose reduction (30 mg edoxaban once-daily) is determined for subjects with one or more of the following factors:

- Moderate or severe renal impairment (CrCL 15 - 50 mL/min)
- Low body weight: ≤ 60 kg (132 lbs),
- Concurrent use of P-gp inhibitors (please refer to local summary of product characteristics [SmPC] or to the Investigator Brochure [IB], as applicable);

In EU countries, according to SmPC concomitant use of edoxaban with cyclosporine, dronedarone, erythromycin, or ketoconazole requires dose reduction to 30 mg once-daily. Concomitant use of edoxaban with quinidine, verapamil, or amiodarone does not require dose reduction.

For low body weight (≤ 60 kg) present at randomization, the edoxaban dose is reduced permanently and even if the subject gains weight, the edoxaban dose remains reduced. The dose of edoxaban returns to the regular dosage regimen of 60 mg once-daily any time the subject no longer displays any of the other above mentioned factors.

After randomization and in subjects without dose reduction, if subject's:

body weight drops to ≤ 60 kg and the body weight change is > 10% of the subject's baseline body weight, then the

edoxaban dose is reduced (i.e. to 30 mg once-daily) permanently.

CrCL becomes 15 to 50 mL/min and the CrCL change is > 20% of the subject's baseline CrCL, then the edoxaban dose is reduced.

- = Develops the need for concomitant treatment with P-gp inhibitors (except quinidine, verapamil or amiodarone), then the edoxaban dose is reduced (i.e. to 30 mg once-daily).

The dose of 15 mg edoxaban once-daily is not indicated as monotherapy and is solely provided as part of transition from edoxaban 30 mg at the end of study (see Section 5.3.3).

VKA: Oral, VKA of choice, as pre-defined per country, with once-daily dosing for target INR between 2.0 to 3.0, inclusive.

VKA is supplied as commercially available tablets of the preferred VKA for each selected country participating in the study, being either:

- Warfarin: 1 and 2.5 mg tablets.
- Phenprocoumon: 3 mg tablets.
- Fluindione: 20 mg tablets(exclusive to France).
- Acenocoumarol: 4 mg tablets.

The Investigator monitors the INR and adjusts the VKA dose to maintain the INR within target. It is the Investigator's responsibility to collect monthly INR assessments and record these throughout the study.

P2Y₁₂ antagonist:

- Clopidogrel 75 mg, oral commercially available tablets.

Subjects receive clopidogrel 75 mg once-daily according to the prescribing information, or in the presence of a documented clinical need (e.g. but not restricted to known clopidogrel non-responder), either

- o Prasugrel 5 or 10 mg, oral commercially available tablets.

Subjects receive prasugrel 10 mg once-daily or prasugrel 5 mg once-daily if ≥ 75 years of age or ≥ 60 kg (132 lb), according to the prescribing information.

- o Ticagrelor 90 mg, oral commercially available tablets.

Subjects receive ticagrelor 90 mg twice-daily according to the prescribing information.

Aspirin (ASA): 100 mg, oral commercially available tablets.

Subjects assigned to the VKA-based regimen receive 100 mg once-daily of ASA. In subjects assigned to the edoxaban-based regimen ASA is not allowed.

Sponsor supplies participating sites with study medication, consisting of edoxaban, VKA (country pre-defined), P2Y₁₂ antagonist (clopidogrel, prasugrel or ticagrelor), and ASA. Please refer to the local SmPC or IB for edoxaban as applicable and to the SmPC of each other study medication.

All dosage adjustments are implemented through the IXRS. The IXRS provides the appropriate drug supply kit number based on the subject's information as provided by the Investigator.

Study Endpoints:

Primary endpoint:

The primary endpoint is the composite of major or clinically relevant non-major bleeding (MCRB) defined according to the ISTH bleeding definitions, analyzed as time to first occurrence of any component.

Secondary endpoints are defined as:

- Main efficacy endpoint (MEE), defined as the composite of cardiovascular (CV) death, stroke, systemic embolic events (SEE), spontaneous myocardial infarction (MI) and definite stent thrombosis (as per ARC consensus definitions).
- Net clinical benefit (NCB), defined as the composite of CV death, stroke, SEE, spontaneous MI, definite stent thrombosis and ISTH-defined major bleeding.
- Main thromboembolic event, defined as composite of cardiac or thromboembolic death (thromboembolic death considered to be thromboembolic in origin (including thromboembolic stroke, pulmonary embolism, any other

systemic embolism), ischemic stroke, SEE, spontaneous MI and definite stent thrombosis.

- ISTH-defined major bleeding
- Any bleeding defined as the composite of major, clinically relevant non-major and minor bleeding (ISTH definition)

- - -- Symptomatic-intracranial-hemorrhage.OGH) -----

Composite of stroke and SEE

Composite of all-cause death, stroke, SEE, spontaneous MI and definite stent thrombosis

Composite of CV death, spontaneous MI and definite stent thrombosis

- The single components of the composite primary and secondary endpoints mentioned above are explored, as well as specific subcategories (e.g., hemorrhagic, ischemic and undetermined stroke)

Safety parameters such as (serious) adverse events, laboratory parameters, ECG and vital signs.

All secondary endpoints are analyzed as time to first occurrence of any of its components.

Bleeding events are also classified according to Bleeding Academic Research Consortium (BARC) and Thrombolysis in Myocardial Infarction (TIMI) classifications for descriptive purposes only. All suspected bleeding events are adjudicated by the CEC in a blinded manner.

All events are also sub-categorized into fatal and non-fatal.

For all endpoints blindly adjudicated by the CEC, the CEC's interpretation prevails and is used in the statistical analyses.

Planned Sample Size: The plan is to enroll 1500 subjects (750 per arm).

Based on a review of available safety data, the estimated one-year event rate of the primary endpoint (MCRB, i.e. ISTH major or clinically relevant non-major bleeding) under the VKA-based antithrombotic regimen is 24%. The edoxaban-based antithrombotic regimen is anticipated to reduce the one-year incidence to 18% (a relative risk (RR) of 0.75). Under the assumption of an exponential distribution, the hazard ratio equals 0.7231. The accrual of 2 x 712 evaluable subjects provides 80% power to demonstrate superiority of the edoxaban-based antithrombotic regimen over the VKA-based antithrombotic

regimen at a two-sided $\alpha=0.05$. To compensate for censoring, the final sample size is set at 2 x 750 subjects.

Statistical Analyses: Four analysis sets are defined:

- The *Intention-to-treat (ITT) analysis set* consists of all randomized subjects irrespective whether they received a single dose of the randomized study regimen or not.
- The *Modified Intention-to-treat (mITT) analysis set* consists of all randomized subjects who received at least one dose of study edoxaban or study VKA according to IXRS assignment.
- The *Per Protocol (PP) analysis set* consists of all randomized subjects who received at least one dose of the study regimen according to IXRS assignment and do not have any of the following major protocol violations:
 - A major violation of the inclusion criteria
 - An unequivocal violation of the exclusion criteria, (for more details, see Section 11.1.3)
- The *Safety (SAF) analysis set* consists of all randomized subjects who received at least one dose of the study edoxaban or study VKA according to IXRS assignment.

Definition of terms:

'Overall Study Period': This period is defined as the time from the reference date (date and time of randomization or date and time of first study edoxabari or study VKA intake) to Day 365.

'Overall Study Period + 30 days': This period is defined as the time from the reference data (date and time of randomization or date and time of first study edoxaban or study VKA intake) to Day 395.

'Initial dose to Final Dose + 30 days': This period is defined as the time-period between the date and time of initial dose of study edoxaban or study VKA and the date of final dose of study edoxaban or study VKA plus 30 days, including study regimen interruptions.

The main analysis of all adjudicated primary and secondary exploratory endpoints will be based on ITT analysis set and taking the first adjudicated event during the 'overall study period' into account.

For each of the primary and secondary exploratory endpoints, appropriate summary statistics (e.g. event rate) including 95% CI will be provided.

For each of the endpoints, the time from reference date to the first occurrence of an event (based on CEC adjudication), is analyzed using a Cox proportional hazard model with treatment regimen as a factor and all the stratification factors from the randomization (IXRS) as covariates, to provide point estimates and 95% Confidence Interval (CI) for the hazard ratio (HR). Depending on the analysis period used in the statistical analysis, subjects without an occurrence of an event will be censored at the last date of the analysis period or at the last date of known outcomes status. The latter is determined on an individual basis for subjects with incomplete follow-up.

For time to first event analyses based on the 'overall study period', cumulative event rates over time are summarized using the Kaplan-Meier method.

There are two primary hypotheses for the primary endpoint to be tested in this study.

- The edoxaban-based antithrombotic regimen is non-inferior to the VKA-based antithrombotic regimen with regards to MCRB.
- The edoxaban-based antithrombotic regimen is superior to the VKA-based antithrombotic regimen with regards to MCRB.

These two hypotheses are tested in a hierarchical manner, non-inferiority followed by superiority to control the type-I error rate, with adequate power for each of the two hypotheses.

The *primary analysis to show non-inferiority* will be based on first occurrence of an (adjudicated) MCRB that occurred during the 'overall study period' for all subjects belonging to the ITT analysis set and applying the aforementioned statistical method. The edoxaban-based regimen will be considered non-inferior to the VKA-based regimen, if the upper boundary of the two-sided 95% CI for HR falls below 1.20.

The *primary analysis to show superiority* will be based on first occurrence of an (adjudicated) MCRB that occurred during the 'overall study period' for all subjects belonging to the ITT analysis set and applying the aforementioned statistical method. The edoxaban-based regimen will be compared with the VKA-based regimen for superiority only if the non-inferiority of the

edoxaban based regimen is established first. The edoxaban-based regimen will be considered superior to the VKA-based regimen, if the upper boundary of the two-sided 95% CI for HR falls below 1.00.

To evaluate the robustness of the primary analysis, the analysis will be repeated using the mITT and PP analysis set. In addition, the statistical results based on the following analysis periods: 'initial dose to final dose+ 30 days', 'overall study period+ 30 days' will be presented but should be interpreted in a more descriptive way.

The *main analysis for all secondary exploratory endpoints* will be based on first occurrence of an (adjudicated) endpoint during the 'overall study period' for all subjects belonging to the ITT analysis set and applying the aforementioned statistical method.

There will be no formal statistical testing for secondary exploratory endpoints. HRs, CI and p-values are provided but should be interpreted in a purely descriptive exploratory manner.

All details of the statistical analysis will be described in a statistical analysis plan (SAP).

TABLE OF CONTENTS

INVESTIGATOR AGREEMENT..... 2

PROTOCOL SYNOPSIS 3

TABLE OF CONTENTS 17

LIST OF IN-TEXT TABLES..... 24

LIST OF IN-TEXT FIGURES 25

LIST OF AUBREVIATIONS..... 26

1. INTRODUCTION AND BACKGROUND INFORMATION 29

1.1. Data Summary..... 30

1.1.1. Investigational Product..... 30

1.1.1.1. Name 30

1.1.1.2. Description 30

1.1.1.3. Intended Use Under Investigation..... 30

1.1.1.4. Nonclinical Studies 30

1.1.1.5. Clinical Experience..... 30

1.2. Study Rationale 32

1.2.1.1. Dose rationale 32

1.3. Risks and Benefits for Study Subjects 32

1.4. Compliance Statement, Ethics and Regulatory Compliance 33

1.4.1. Subject Confidentiality..... 33

1.4.2. Informed Consent (IC) Procedure 33

1.4.3. Regulatory Compliance..... 34

2. STUDY OBJECTIVES AND HYPOTHESES 35

2.1. Study Objectives..... 35

2.1.1. Primary Objectives..... 35

2.1.2. Secondary Exploratory Objectives 35

2.1.3. Other Objectives..... 36

3. STUDY DESIGN..... 37

3.1. Overall Plan..... 37

4. STUDY POPULATION 39

4.1. Emollment. 39

4.1.1. Inclusion Criteria..... 39

4.1.2.	Exclusion Criteria.....	40
4.2.	Screening failures.....	41
4.3	Removal of Subjects from Therapy	42
4.3.1	Reasons for Withdrawal/Early Discontinuation.	42
4.3.2	Withdrawal Procedure	43
4.3.3	Study or Site Termination	43
4.4.	Subject Replacement	44
4.5.	Subject Re-screening Procedures.....	44
S.	TREATMENT REGIMENS ADMINISTERED.....	45
5.1.	Method of Assigning Subjects to Treatment Regimens.....	45
5.2.	Study Treatment Regimens	45
5.2.1.	Edoxaban-based regimen for 12 months.....	45

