5. TREATMENT REGIMENS ADMINISTERED

5.i. Method of Assigning Subjects to-Treatment Regimens

After the IC has been signed and eligibility confirmed, the Investigator contacts the IXRS to assign an individual study identification number.

The Investigator should be prepared to provide subject information, including, but not limited to: age, body weight, clinical presentation [ACS or stable coronary artery disease (CAD)], CrCL using Cockcroft-Gault formula (see Section 17.6) and whether the subject is taking concomitant P-gp inhibitors requiring edoxaban dose reduction (according to local SmPC or 1B as applicable).

Randomization is stratified by clinical presentation (ACS or stable coronary disease), requirement for dose adjustment of edoxaban, and by geographical region (i.e. Latin America, Western Europe, Eastern Europe, Asia, as applicable).

Subjects will be assigned randomly via the above mentioned IXRS such that the study has a 1:1 ratio of subjects in the two antithrombotic treatment regimens.

The specifications for generation of the randomization schedule will be prepared by the study biostatistician and the IXRS vendor. An independent biostatistician, not otherwise part of the study team, will generate the randomization schedule. For this study, the randomization schedule refers to a list that includes the subject identification number (ID), randomization block number, and randomization treatment.

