5.3.1. Dose

Edoxaban 60 mg once-daily.

At randomization, the recommended dose of edoxaban is 30 mg once-daily in subjects with 1 or more of the following factors:

- Moderate or severe renal impairment (calculated CrCL 15 - 50 mL/min),
- Low body weight of < 60 kg (132 lbs),
- Concurrent use of P-gp inhibitors (please refer to local SmPC or to 1B, as applicable).

In EU countries, according to SmPC concomitant use of edoxaban with cyclosporine, dronedarone, erythromycin, or ketoconazole requires dose reduction to 30 mg once-daily. Concomitant use of edoxaban with quinidine, verapamil, or amiodarone does not require dose reduction.

All edoxaban dosage adjustments will be implemented through the IXRS. The IXRS will provide the appropriate drug supply kit number.

If low body weight (< 60 kg) present at randomization, the edoxaban dose is reduced permanently and even if the subject gains weight, the edoxaban dose remains reduced.

The dose of edoxaban returns to the regular dosage regimen of 60 mg once-daily any time the subject no longer displays any of the other above mentioned factors.

After randomization and in subjects without dose reduction, if subject's:

body weight drops to < 60 kg and the body weight change is > 10% of the subject's baseline body weight, then the edoxaban dose is reduced (i.e., to 30 mg once-daily) permanently.

CrCL becomes 15 to 50 mL/min and the CrCL change is > 20% of the subject's baseline CrCL, then the edoxaban dose is reduced.

Develops the need for concomitant treatment with certain P-gp inhibitors which require edoxaban dose adjustment, then the edoxaban dose is reduced (i.e., to 30 mg once-daily).

The dose of 15 mg edoxaban once-daily is not indicated as monotherapy and is solely provided as part of transition from edoxaban 30 mg at the end of study (see Section 5.3.3).

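### The synopsis and Section 5.3.1 give different rules for reducing edoxaban when a P-gp inhibitor is started after randomization

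*Combined protocol and SAP*

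**What the plan says.** **P-gp inhibitors at randomization.** The sections agree. The synopsis (Dosage Form, Dose, and Route of Administration) lists "Concurrent use of P-gp inhibitors (please refer to local summary of product characteristics [SmPC" and goes on to name the IB. Section 5.3.1 lists "Concurrent use of P-gp inhibitors (please refer to local SmPC" and does the same. Both then give the same EU lists: cyclosporine, dronedarone, erythromycin and ketoconazole require reduction; quinidine, verapamil and amiodarone do not. Section 5.1 asks the site to tell the IXRS "whether the subject is taking concomitant P-gp inhibitors requiring edoxaban dose reduction (according to local SmPC or 1B as applicable", and Section 6.1.2 uses the same basis.

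**P-gp inhibitors after randomization.** The sections differ. The synopsis has "Develops the need for concomitant treatment with P-gp inhibitors (except quinidine, verapamil or amiodarone), then the edoxaban dose is reduced", with no regional limit. Section 5.3.1 has "Develops the need for concomitant treatment with certain P-gp inhibitors which require edoxaban dose adjustment, then the edoxaban dose is reduced". That sentence gives no list of its own, but the factor list in the same section and Section 5.10 both refer to the local SmPC or IB. The Figure 3.1 note also limits the trigger to certain inhibitors.

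**Weight.** The synopsis has "Low body weight: ≤ 60 kg (132 lbs" and repeats the inclusive sign in its permanence rule and its post-randomization rule. The Figure 3.1 note is inclusive too. Section 5.3.1, in the text supplied, has "Low body weight of < 60 kg (132 lbs" and the strict sign in the same three places.

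**The concern.** The two post-randomization P-gp rules have opposite defaults. Under the synopsis a new inhibitor triggers reduction unless it is one of three drugs. Under Section 5.3.1 it triggers reduction only if the label requires it. The synopsis also departs from its own baseline rule: a drug already in use at randomization is judged by the local label, while the same drug started later is judged by the three-drug exemption.

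Section 1.1.1.5 says that drugs with P-gp inhibitory effects may alter edoxaban exposure, and the primary endpoint is bleeding. A site could therefore find support in the protocol for either dose. Section 6.4 asks sites to report dosing deviations, and with two rules there is no single standard for deciding what counts as one.

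**Working it through.** **1. The plan's own figures.** No figure in the plan is derived from the dose triggers. The sample size reproduces without them:
- HR = ln(1 − 0.18)/ln(1 − 0.24) = 0.7231, as stated.
- The Schoenfeld formula at 80% power and two-sided 0.05 gives 299 events. Dividing by the mean event probability (0.24 + 0.18)/2 = 0.21 gives 1424 subjects, or 712 per arm, as stated.
- Non-inferiority at HR 0.88: the edoxaban event rate is 1 − 0.76^0.88 = 0.2146, so 1500 subjects give 1500 × (0.24 + 0.2146)/2 = 341 events. Power = Φ(√(341/4) × ln(1.20/0.88) − 1.96) = 81.7%, against 82% stated.

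None of these inputs involves P-gp use or body weight.

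**2. The P-gp rules side by side**, for a subject on 60 mg with no other reduction factor who starts an inhibitor after randomization:

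| New drug | Synopsis | Section 5.3.1 with 5.10 |
|---|---|---|
| Cyclosporine, dronedarone, erythromycin, ketoconazole (EU) | 30 mg | 30 mg |
| Quinidine, verapamil, amiodarone (EU) | 60 mg | 60 mg |
| Inhibitor outside these seven, label requires no reduction | 30 mg | 60 mg |
| Inhibitor outside these seven, label requires reduction | 30 mg | 30 mg |
| Quinidine, verapamil or amiodarone where a local label or IB requires reduction | 60 mg | 30 mg |

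The third row is a conflict in any region, the EU included. The fifth is hypothetical on these documents. Enrolment includes Asia-Pacific and the named lists are given for EU countries only, but no such local label is described.

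**3. Does the IXRS settle it?** Dose changes go through the IXRS, which acts on what the investigator provides. In Section 6.1.2 the P-gp item is a conclusion (an inhibitor that requires reduction), not a drug name. The follow-up lists in Sections 6.2.1 to 6.2.3 record concomitant medications and, at on-site visits, creatinine clearance, but no P-gp status item. The site must first judge whether the new drug counts, and that is where the two rules part.

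**4. Reach into the analysis.** Section 11.4 uses the stratification factors from randomization as Cox covariates. The at-randomization P-gp rule is the same throughout, so this conflict moves no subject between strata and changes no covariate.

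**5. Weight, read literally**, with no other reduction factor at randomization:

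| Weight | Synopsis | Section 5.3.1 |
|---|---|---|
| 59.9 kg | 30 mg | 30 mg |
| 60.0 kg | 30 mg | 60 mg |
| 60.1 kg | 60 mg | 60 mg |

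After randomization the rule also needs a change of more than 10%, so the difference matters only at exactly 60 kg reached from a baseline above 60/0.9 = 66.7 kg.

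The documents give no weight distribution. Assuming whole-kilogram recording and a normal distribution, the share recorded at 60 kg is 1.3% with mean 78 and SD 15 kg (0.0129 × 750 ≈ 10 edoxaban subjects), and 2.9% with mean 66 and SD 12 kg (0.029 × 750 ≈ 22). These are upper figures, since some of those subjects would have another reduction factor.

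**The case against.** The strongest reply is that one synopsis bullet is the outlier. Section 5.3.1, Section 5.10 and the Figure 3.1 note all limit the trigger to certain inhibitors. The synopsis itself refers to Section 5.3.1 and to the local label, the seven named drugs come out the same in the EU, and the IXRS implements every dose change. Most of this stands, and it makes the conflict narrow. It does not remove it. The synopsis treats its own dosage section and Section 5.3.1 as joint sources, nothing in the text supplied says which prevails, and the IXRS depends on the site's judgement. The two rules differ in words, so a fault in reading the PDF cannot explain them.

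On weight, the reply is that the strict sign in Section 5.3.1 may be a lost ≤. That is a fair caution. Table 5.2 has INR < 2.5 where a Schedule of Events footnote has ≤ 2.5 for the same step, and the edoxaban-to-VKA transition text in Section 5.3.3 has an INR of 2.0 with no sign at all. Against that, the strict sign appears in all three places in Section 5.3.1. Only the source PDF can decide.

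A reader might also infer that a 60 kg subject falls into a different randomization stratum according to which section the site follows. The documents do not support this. Sites enter body weight and the IXRS returns the dose-reduction flag, so one programmed rule applies to everyone in both arms. What is open is which operator was programmed. Nor do they support the inference that sites would code P-gp status differently at randomization because the sections conflict, since on that point the sections agree.

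**Conclusion.** The post-randomization P-gp rule contradicts itself between the synopsis and Sections 5.3.1 and 5.10, and the synopsis contradicts its own at-randomization rule. The consequence is a possible 30 mg against 60 mg difference for edoxaban subjects who start an inhibitor outside the seven named drugs whose label requires no reduction. A conflict in the other direction would need a local label or IB that requires reduction for one of the three exempted drugs, which the documents neither confirm nor exclude. How often either occurs cannot be estimated from the documents.

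This is a defect in dosing instructions that bears on exposure and on judging deviations. It is not a threat to the primary analysis. The weight discrepancy is conditional on the PDF and limited to a recorded weight of exactly 60 kg with no other reduction factor. Its counts rest wholly on assumed distributions.

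**What to change.** Reconcile the synopsis, the Figure 3.1 note and Sections 5.3.1 and 5.10 to one P-gp trigger rule that covers both randomization and follow-up. Check the weight signs in Section 5.3.1 against the source PDF and, if the difference is real, state one inequality everywhere. Confirm that the IXRS specification matches the reconciled text for both triggers. Which rule and which inequality apply is for the clinical team.

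The cost is amendment wording and a specification check, with no extra visits or samples. If the IXRS proves not to match, correcting and revalidating it is a further cost. A country-specific list of triggering inhibitors within the IXRS would remove the site's judgement, but it is optional and would also need a system change.
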